9.2. Data Management

All missing and ambiguous data will be queried. Information will be handled as dictated by the Data Protection Act, 2018, and General Data Protection Regulations. All identifiable data including clinical records and images will form part of the patient's clinical record and so will be stored in NHS hospital servers in the usual way and will be subject to standard information governance procedures and care. If a participant or their consultees decide to withdraw, data will be retained and analysed as part of the study.

Prior to any research-related analysis (i.e. beyond clinical care) all scans and investigations and any data arising will be pseudo-anonymised with a specific numerical code (study number). The details of which patient matches which code will be stored on an NHS computer system, subject to standard information governance procedures and care. Hospital numbers may also be linked to the study number on encrypted university computers, protected with at least AES 256-bit encryption in addition to standard university password-

Study name:	Traumatic brain inju	raumatic brain injury related changes in military veterans					
Protocol version number:	3.0	version date:	11 October 2023	Page:	17 of 22		

controlled account access. Anonymised data will be shared in a TBI data hub that is being developed by us with collaborators in Cambridge for future research, which will require a data request and scrutiny from a panel of reviewers including PPIE representatives with lived experience of TBI.

9.3. Archiving

Documents will be archived following the University of Birmingham Code of Practice for Research. It is the responsibility of the Principal Investigator to ensure all essential trial documentation and source documents (e.g. signed Informed Consent Forms, Investigator Site Files, Pharmacy Files, participants' hospital notes, copies of CRFs etc.) at their site are securely retained for at least 10 years.

10. Quality control and quality assurance

10.1. Site Set-up and Initiation

All participating Principal Investigators will be asked to sign Trust documentation and supply a current CV and evidence of Good Clinical Practice (GCP) Training to the Trust Research and Development Department. All members of the site research team will also be required to sign a site signature and delegation log. Prior to commencing recruitment all sites will undergo a process of initiation and will have completed GCP training. Key members of the site research team will be required to attend either a meeting covering aspects of the trial design, protocol procedures, Adverse Event reporting, collection and reporting of data and record keeping. Sites will be provided with an Investigator Site File containing essential documentation, instructions, and other documentation required for the conduct of the trial. The Trust Research and Development Department must be informed immediately of any change in the site research team.

10.2. Monitoring

There is no specific monitoring requirement. Continuous data monitoring will ensure the credibility of the data. Source documents will be available for 'on-site monitoring' by the host Trust and external agencies.

10.3. Audit and Inspection

The Principal Investigator will permit study-related monitoring, quality checks, audits, ethical reviews, and regulatory inspection(s) at their site, providing direct access to source data/documents. The Principal Investigator will comply with these visits and any required follow up.

10.4. Notification of Serious Breaches

The sponsor is responsible for notifying the REC of any serious breach of the conditions and principles of GCP in connection with the study or the protocol relating to the study. Sites should therefore notify the Research Governance Team at the University of Birmingham of any suspected serious breach of GCP and/or the protocol.

A copy is sent to the University of Birmingham Clinical Research Compliance Team at the time of reporting to the REC.

11. End of Trial Definition

The end of study will be 2 years after initiation or 6 months after recruitment of the last patient, whichever is the earlier. The CI will notify the REC and sponsor of the end of the study.

A copy of the end of study notification as well as the summary report is also sent to the University of Birmingham Research Governance Team at the time of sending to the REC.

Study name:	Traumatic brain injury related changes in military veterans					
Protocol version number:	3.0	version date:	11 October 2023	Page:	18 of 22	

12. Statistical Considerations

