4.1. Inclusion Criteria for acute TBI group

- 1. Over the age of 18
- 2. Must have 2 eyes

3. Not all participants will have capacity to consent (e.g. moderate to severe TBI). For these participants, they will require a personal or nominated consultee.

- 4. Willing and able or consented by consultees to follow the protocol
- 5. Moderate or severe head injury requiring admission to the Queen Elizabeth Hospital within the prior 14 days

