6.1. Summary of assessments

Figure 2. Assessments planned for acute TBI patients

		TRI	AL PERIOD	
	Enrolment	Initial assessment (may be at enrolment)	Post-allocation (monitoring interval clinically determined)	Close-out
TIMEPOINT**	-t1	Contact 1 (0-14 days post head injury or at enrolment)	Contact 2-5 (1, 3, 6 and 9 months after head injury or enrolment)	Contact 6 (12 months after head injury)
ENROLMENT:				
Eligibility screen	Х			
Informed consent	Х			
ASSESSMENTS:				
Collect blood and saliva		X (face to face)	X (1 and 6 months only, face to face)	X (face to face)
Visual function tests (e.g. visual acuity and field tests, optical coherence tomography (OCT), OCT angiography, pupillometry, Email saccadic latency and autorefraction.		X (face to face)	X (1 and 6 months only, face to face)	X (face to face)
Mental health outcomes (social and occupational functioning assessment)		X (face to face and remotely)	X (1 and 6 months only, face to face and remotely)	X (face to face or remotely)
Self-reported measures collected by post (e.g. BIVSS (visual impairment, General anxiety disorder, PTSD, Suicidal behaviour, alcohol use and quality of life		X (all collected remotely)	X (1, 3, 6 and 9 months, all collected remotely)	X (all collected remotely)
Head injury outcome				х

Study name:	Fraumatic brain injury related changes in military veterans					
Protocol version number:	3.0	version date:	11 October 2023	Page:	13 of 22	

		TRI	AL PERIOD	
	Enrolment	Initial assessment (may be at enrolment)	Post-allocation (monitoring interval clinically determined)	Close-out
TIMEPOINT**	- t 1	Contact 1 (at enrolment)	Contact 2-4 (3, 6 and 9 months enrolment)	Contact 5 (12 months after enrolment)
ENROLMENT:				
Eligibility screen	Х			
Informed consent	Х			
ASSESSMENTS:				
Collect blood and saliva		X (face to face)	X (at 6 months only, face to face)	X (face to face)
Visual function tests (e.g. visual acuity and field tests, optical coherence tomography (OCT), OCT angiography, pupillometry, Email saccadic latency and autorefraction.		X (face to face)	X (at 6 months only, face to face)	X (face to face)
Mental health outcomes (social and occupational functioning assessment)		X (face to face and remotely)	X (at 6 months only, face to face or remotely)	X face to face or remotely)

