Self-reported measures collected by post (e.g. BIVSS (visual impairment, General anxiety disorder, PTSD, Suicidal behaviour, alcohol use and quality of life		X (all collected remotely)	X (at 3, 6 and 9 months, all collected remotely)	X (all collected remotely
Head injury outcome				Х

Figure 3. Assessments planned for military veterans group

Study name:	Traumatic brain injury related changes in military veterans					
Protocol version number:	3.0	version date:	11 October 2023	Page:	14 of 22	

-igure 4. Assessments pl		,,,,,,,,,,,,,,,,,,,,,,,,,,,,,,,,,,,,,,,	AL PERIOD	
	Enrolment	Initial assessment (may be at enrolment)	Post-allocation	
TIMEPOINT**		Contact 1 (single assessment point)	Contact 2 (6 months after enrolment)	
ENROLMENT:				
Eligibility screen		Х		
Informed consent		Х		
ASSESSMENTS:				
Collect blood and saliva		X (face to face)	X (face to face)	
Visual function tests (e.g. visual acuity and field tests, optical coherence tomography (OCT), OCT angiography, pupillometry, Email saccadic latency and autorefraction		X (face to face)	X (face to face)	
Mental health outcomes (social and occupational functioning assessment)		X (face to face and remotely)	X (face to face or remotely)	
Self-reported measures collected by post (e.g. BIVSS (visual impairment, General anxiety disorder, PTSD, Suicidal behaviour, alcohol use and quality of life		X (all collected remotely)	X (6 months, all collected remotely)	
Head injury outcome		N/A		

Figure 4. Assessments planned for non-head injury control group

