6.2 Schedule of Assessments and Risks

Screening/enrolment

Study name:	y name: Traumatic brain injury related changes in military veterans						
Protocol version number:	3.0	version date:	11 October 2023	Page:	15 of 22		

Patients' eligibility and willingness to participate will be assessed as described above in the section on consent.

Clinical assessments (Contact 1-6)

All participants recruited will undergo collection of blood and saliva to detect fluid biomarkers of injury, visual function assessments, mental health status and PROMs. Assessments at the 12 month point will be conducted face to face where possible, but where patients are unable to attend (e.g. have moved away) will be conducted remotely. Study time points for visits 2-6 will allow a 10% variation from stated timings. Face to face visits will therefore be at enrolment, 1 month (acute TBI only), 6 months (all patients) and 12 months (acute TBI and veterans where possible).

Taking blood using a needle is uncomfortable, can cause bruising and bleeding and sometimes fainting. Only trained staff will collect the blood samples to ensure this does not occur. Saliva will be collected in a tube and is not invasive and should not cause any problems.

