Visual function tests: visual acuity measurements with normal refractive correction and pinhole where vision is less than logMAR 0 monocularly; colour vision assessed monocularly using Colour Assessment and Diagnosis (CAD); visual field assessed using the SITA Fast 24-2 Humphrey Visual Field-testing algorithm, contrast sensitivity test by monocular reading Pelli-Robson contrast chart or Acuity Plus (on the CAD), pupil assessment using a pupillometer and visual focussing mechanism and ocular motility are assessed using autorefraction and Email saccadic latency assessment respectively. OCT will be used to image the retina and optic nerve head. Dilating drops (tropicamide 0.5%) may be applied where necessary to assist the assessment where this would not interfere with assessment by the neurosurgical team (e.g. when an inpatient on neuroobs). All visual function assessments and OCT imaging will be carried out at contact points 1 and 3 and where possible at close out (contact 6) when the patient is able to cooperate, although all subjective assessments may not be possible in the acute phase after TBI. Additionally, head injury outcome (i.e. Glasgow outcome scale (daily living assessment by a physician); Mayo-Portland Adaptability Inventory (physical and daily living assessment by a physician) will be assessed at the final visit as part of routine care. There are no risks associated with these tests as they are an assessment of patient's abilities by a physician.

We will use eye drops as per standard care to dilate patient eyes, as is routine. This may mean that patient eyes will be more sensitive to light and can take up to 6 hours to become normal. We will recommend the use of sunglasses to minimise the impact of light to patient eyes. We will also recommend that patients do not drive and that someone accompanies them. We will refund travel expenses.

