12.1. Definition of Outcome Measures

The primary outcome measure will be the longitudinal changes in mental health status and quality of life. This will be defined using parameters outlined in the clinical assessments section. The secondary outcome will be longitudinal changes in fluid biomarkers of injury (e.g. glial fibrillary acidic protein (GFAP), S100 β , tumor necrosis factor- α and myelin basic protein), visual function (e.g. visual acuity, contrast acuity, colour vision, visual field pupil reaction, focussing mechanism and eye movements, and brain injury outcomes assessed using the Glasgow outcome scale and Mayo-Portland Adaptability Inventory), other mental health status and PROMs.

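### The end-of-study rule in Section 11 can close the study before the 9- and 12-month contacts of acute TBI participants and veterans who enrol late

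*Protocol*

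**What the plan says.** Section 11 (End of Trial Definition) reads: "The end of study will be 2 years after initiation or 6 months after recruitment of the last patient, whichever is the earlier". The Chief Investigator then notifies the ethics committee and the sponsor that the study has ended.

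Section 6.1 sets the visits by group:

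- Acute TBI (Figure 2): contacts at 1, 3, 6 and 9 months, then close-out at "Contact 6 (12 months after head injury").
- Veterans (Figure 3): contacts at 3, 6 and 9 months, then close-out at "Contact 5 (12 months after enrolment").
- Controls (Figure 4): last contact at "Contact 2 (6 months after enrolment").

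In Figures 2 and 3 the close-out column includes blood and saliva, visual tests, SOFAS, the self-reported measures and head injury outcome. Head injury outcome is marked in no other column. Section 6.2 agrees: the Glasgow outcome scale and the Mayo-Portland inventory "will be assessed at the final visit as part of routine care". Section 6.2 also gives the visit window: "Study time points for visits 2-6 will allow a 10% variation from stated timings".

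On outcomes, Section 12.1 says: "The primary outcome measure will be the longitudinal changes in mental health status and quality of life". It lists the two head injury scales among the secondary outcomes. Section 12.2 compares Contact 1 with Contacts 2 to 6.

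**The concern.** A rule that may end the study 6 months after the last recruit cannot hold a 12-month schedule for someone recruited near the end. The 2-year limit can only shorten the time further, because the earlier of the two dates applies. Nothing in the protocol says that follow-up continues after the end of study.

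At stake are visits that cannot be recovered once the study has closed. An affected participant has no head injury outcome at all and no 12-month value on the primary measures. The loss is set by enrolment date and falls on the acute TBI and veteran groups, because the control schedule stops at 6 months.

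**Working it through.** **Inputs from the protocol**

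- End of study: the earlier of 24 months after initiation and 6 months after the last recruit (Section 11).
- Close-out: 12 months after injury (acute TBI) or after enrolment (veterans) (Section 6.1).
- Window: 10% (Section 6.2). The close-out may fall between 12 − 1.2 = 10.8 and 12 + 1.2 = 13.2 months. The 6-month visit may fall as late as 6 + 0.6 = 6.6 months.
- Enrolment lag in the acute group: up to 14 days, from "Moderate or severe head injury requiring admission to the Queen Elizabeth Hospital within the prior 14 days" (Section 4.1) and the 0–14 day approach period in Section 5.
- Group size: 30 (Section 12.2).

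**The plan's own figure.** The protocol states neither a recruitment period nor a share reaching month 12, so there is none to reproduce. Its one completer count, 24 of 30, does reproduce (30 × 0.8 = 24). It belongs to the retinal nerve fibre layer (RNFL) calculation and uses a loss rate seen at 3 months.

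**Assumptions for the base case.** Recruitment lasts R months, is uniform from initiation, and runs over the same period in all groups.

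**Formula.** The study ends at E = min(24, R + 6). A participant enrolled at month t loses a visit due at month v if t + v > E. The share lost is [R − (E − v)] / R, held between 0 and 1. For v = 12 this is 6/R when R lies between 6 and 18, and (R − 12)/R when R exceeds 18. For v = 10.8 it is 4.8/R up to R = 18, and (R − 13.2)/R beyond.

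| R (months) | E (months) | Lost, visit at exactly 12 | Lost, earliest in-window visit (10.8) |
|---|---|---|---|
| 6 | 12 | 100% | 80% |
| 9 | 15 | 67% | 53% |
| 12 | 18 | 50% | 40% |
| 15 | 21 | 40% | 32% |
| 18 | 24 | 33% | 27% |
| 20 | 24 | 40% | 34% |
| 24 | 24 | 50% | 45% |

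The minimum is at R = 18: 6/18 = 33.3%, or 4.8/18 = 26.7% if every close-out is brought to the start of its window. That is 10 or 8 of 30 per group. If every acute participant enrols 14 days after injury (0.46 months), the acute-group minimum is 5.54/18 = 30.8%, or 4.34/18 = 24.1% with the window.

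**9-month contact** (v = 9, exact): 3/12 = 25% at R = 12, 3/18 = 17% at R = 18, and (24 − 15)/24 = 37.5% at R = 24.

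**Other accrual patterns, exact 12-month visits**

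- Front-loaded, cumulative share (t/R)^0.5, R = 18: 1 − (12/18)^0.5 = 18%.
- Back-loaded, cumulative share (t/R)^2, R = 18: 1 − (12/18)^2 = 56%.
- Acute TBI and veteran recruitment ends at month T, last control at month 18, so E = 24: loss (T − 12)/T, which is 0% at T = 12, 20% at T = 15 and 25% at T = 16.

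**What does not depend on accrual.** If the last recruit is an acute TBI participant or a veteran, that person always loses both late contacts. The earliest in-window 9-month visit is at 9 − 0.9 = 8.1 months, or about 7.6 after a 14-day lag, and both exceed 6. A control recruited last could also have an in-window visit at 6.6 months, after the study has ended.

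**The case against.** The study is an exploratory pilot. Section 1.2.2 keeps participants who do not complete every stage, Section 5 expects missing data, and Section 6.2 holds the 12-month visit face to face only where possible. The primary outcome has no single time point, and the self-reported measures are also taken at 3, 6 and 9 months (and at 1 month in the acute group), so late recruits still contribute change data. The head injury scales are secondary. If acute TBI and veteran recruitment finished well before control recruitment, there might be no loss at all.

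Much of this stands and limits the damage. It does not remove the conflict. Tolerating patients who cannot complete is different from a rule that prevents completion. The proviso in Section 6.2 concerns attendance in person, since those who cannot attend are assessed remotely. No section sequences recruitment so that controls come last.

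Some stronger readings are tempting but not supported:

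- A reader might infer that at least a third of these participants must lose the close-out. One third is the minimum only for uniform, simultaneous accrual with visits at exactly 12 months. The protocol's own window lowers it to 27%, and some patterns give 0%.
- A reader might infer that the study stops before month 12 for everyone. Early enrolees can finish unless recruitment is very short.
- A reader might set the reduced 12-month numbers against the 24 completers in Section 12.2. That figure concerns RNFL thickness with a 3-month loss rate and is not a 12-month target.
- A reader might infer that the 12-month data are confounded with calendar time. That would need recruits to differ over time, which nothing in the protocol shows.

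**Conclusion.** The concern holds as an internal contradiction: Section 11 does not fit the 9- and 12-month contacts in Sections 6.1 and 6.2 for acute TBI participants and veterans who enrol late, and these sections must be reconciled. What is lost by rule is the 12-month close-out, for the latest recruits the 9-month contact as well, the only Glasgow outcome scale and Mayo-Portland assessments, and the last time point of the primary outcome.

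The size depends on a recruitment period that the protocol does not state. Under steady, simultaneous accrual from initiation the best case is about 27% to 33%, at 18 months of recruitment. It rises to 50% at 12 or 24 months with exact visits. Across other patterns it runs from 0% (acute TBI and veteran recruitment finished by month 12, last control at month 18) to 100% (recruitment within 6 months, exact visits). These shares are scenarios; the contradiction itself needs no assumption about accrual.

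**What to change.** Define the end of study as completion of the last scheduled visit, including its 10% window, of the last participant in any group. This replaces both the 6-month clause and the 2-year limit, and brings the loss by rule to 0% for any recruitment period. Changing only the earlier date to the later one is not enough: under uniform accrual with exact visits it still loses 20% at R = 15, 33% at R = 18 and 25% at R = 24.

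If the 2-year cap must stay, delete the 6-month clause and close recruitment early enough for every window to fall inside the cap: acute TBI and veterans by about month 24 − 13.2 = 10.8, controls by about month 24 − 6.6 = 17.4.

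The cost is a short amendment plus time. If an acute TBI participant or veteran is recruited last, the end moves from R + 6 to R + 12 for recruitment of up to 18 months, which is 6 months more. For R = 24 it moves from month 24 to month 36, which is 12 months more. The window adds up to 1.2 months in either case. Keeping the cap adds no duration but shortens recruitment.

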12.1. Definition of Outcome Measures

The primary outcome measure will be the longitudinal changes in mental health status and quality of life. This will be defined using parameters outlined in the clinical assessments section. The secondary outcome will be longitudinal changes in fluid biomarkers of injury (e.g. glial fibrillary acidic protein (GFAP), S100 β , tumor necrosis factor- α and myelin basic protein), visual function (e.g. visual acuity, contrast acuity, colour vision, visual field pupil reaction, focussing mechanism and eye movements, and brain injury outcomes assessed using the Glasgow outcome scale and Mayo-Portland Adaptability Inventory), other mental health status and PROMs.

12.2. Power Calculation and Statistical Analysis

Data obtained from all clinical examinations and laboratory tests will be compared between the first visit (Contact 1) and the subsequent follow-up visits (Contact 2-6). Many of these data are continuous and normally distributed as well as being repeated measures data of the same subjects. As such, repeated measures ANOVA will be used to determine changes over time. Data that are not normally distributed or numeric will be analysed using non-parametric tests. Linear mixed models, linear regression and analysis of covariance will be used for binary and ordinal outcomes as appropriate. Trial statisticians in the Birmingham Clinical Trials Team will be engaged for further statistical advice, if required.

This is a pilot study to evaluate longitudinal changes in fluid and visual biomarkers of brain injury, mental health status and self-reported quality of life measures in patients with TBI (civilian and military veterans). The sample size is based on:

1) statistical advice that in a pilot / feasibility study, 30 subjects in each group are recommended to allow estimation of the parameters of interest³².

2) Based on Child's et al.³² which showed a difference of 5um in global retinal nerve fibre layer thickness between boxers and controls, an average RNFL thickness of 101. Past experience in the concussion clinic suggests that we are able to follow 80% of patients at the 3-month point (i.e. only 20% lost to follow up). We based the power calculation looking for power to detect a 5um change in the repeated measures, assuming correlation of 0.9 between repeated measures of RNFL thickness (conservative given that in the absence of pathology, RNFL thickness varies very little). Simulated power calculations in R revealed that 24 participants with complete data (recruiting 30 and assuming a 20% drop out) would have >80% power to detect a 2µm change in RNFL thickness and 100% power to detect a 5µm decrease.

13. Ethical Considerations

The study will be performed in accordance with the recommendations guiding physicians in biomedical research involving human subjects, adopted by the 18th World Medical Association General Assembly, Helsinki, Finland, June 1964, amended at the 48th World Medical Association General Assembly, Somerset West, Republic of South Africa, October 1996 (website: http://www.wma.net/en/30publications/10policies/b3/index.html).

The study will be conducted in accordance with the Research Governance Framework for Health and Social Care, the applicable UK Statutory Instruments, (which include the Medicines for Human Use Clinical Trials 2004 and subsequent amendments and the Data Protection Act 2018 and the Human Tissue Act 2008.

Some research participants may receive a new diagnosis of cognitive impairment or PTSD at follow-up. This is of benefit in terms of access to appropriate support services but may have potential harms in terms of withdrawal and acceptance of the diagnosis. We will inform their care team so that they can receive the appropriate support and develop an action plan. If a patient self-reports any suicidal thoughts or behaviours, they will be contacted by the care team to provide further support. In addition, we will provide details of dedicated organisations such as Samaritans, Campaign against living miserably (CALM), Papyrus, Childline or SOS-Silence of Suicide. We will also direct them to contact someone they trust, their GP, call 111 or their mental health crisis team (if they have one) to talk over their issues.

Study name:	Traumatic brain inju	raumatic brain injury related changes in military veterans					
Protocol version number:	3.0	version date:	11 October 2023	Page:	19 of 22		

Before any participants are enrolled into the study, the Principal Investigator is required to obtain local R&D approval. Sites will not be permitted to enrol participants until written confirmation of R&D approval is received by the Principal Investigator.

It is the responsibility of the Principal Investigator to ensure that all subsequent amendments gain the necessary local approval. This does not affect the individual clinicians' responsibility to take immediate action if thought necessary to protect the health and interest of individual participants. Both minor and substantial amendments will be submitted to the sponsor for review and approval prior to submission to the relevant regulatory authorities.

[name] (CI) is a co-founder and a non-executive board member of a University of Birmingham-based spin-off company called Neuregenix Ltd. Neuregenix Ltd is a contract research organisation but will have no part in this study.

14. Confidentiality and Data Protection

Personal data recorded on all documents will be regarded as strictly confidential and will be handled and stored in accordance with the Data Protection Act 2018 and General Data Protection Regulation 2018

Participants will be identified using only their unique study identification number on the Case Report Form and correspondence and all identifiable data retained on Trust computers. No identifiable data will be stored on University of Birmingham servers. Data may be linked to hospital number and name on Trust computers but pseudo-anonymised on University of Birmingham secure servers protected by AES 256-bit encryption. No patient identifiable data will be stored on individual computers. Data transfers between the University of Birmingham and UHB will conform to secure University of Birmingham and NHS policies.

All questionnaires will have a cover sheet that will include a unique participant ID number only. If a patient accidently includes their name, this will be redacted on receipt.

The Investigator must maintain documents (e.g. Participant Identification Logs) in strict confidence. In the case of specific issues and/or queries from the regulatory authorities, it will be necessary to have access to the complete trial records, provided that participant confidentiality is protected. These will be stored in locked cupboards in University of Birmingham premises and access controlled by the Investigator.

Representatives of the sponsor may be required to have access to participant's notes for quality assurance purposes but participants should be reassured that their confidentiality will be respected at all times.

After data collection is complete, study data will be anonymised.

15. Insurance and Indemnity

The University has in force a Public Liability Policy and/or Clinical Trials policy which provides cover for claims for "negligent harm" and the activities here are included within that coverage.

With respect to the conduct of the trial at Site and other clinical care of the patient, responsibility for the care of the patients remains with the NHS organisation responsible for the Clinical Site and is therefore indemnified through the NHS Litigation Authority.

The University of Birmingham is independent of any pharmaceutical company, and as such it is not covered by the Association of the British Pharmaceutical Industry (ABPI) guidelines for participant compensation.

Study name:	Traumatic brain injury related changes in military veterans					
Protocol version number:	3.0	version date:	11 October 2023	Page:	20 of 22	

16. Publication Policy

